### **Stage 2: 8-week home evaluation**

After the first clinical assessment, the subject will be sent home with the ssNPA in place for home evaluation purposes for approximately 8 weeks, with two clinical in-person check-ins at weeks 2 and 4. As HUAO often results in obstructive events, both at night and while awake, we anticipate the ssNPA may be used for a large proportion of a 24-hour period in many children. The ssNPA desensitization protocol provides step-by-step instructions on how to help children get comfortable with placement of the device during daytime, after which, they will progress to use the ssNPA at night. Our team will work closely with parents/caregivers to follow instructions in the protocol to achieve adherence to ssNPA during these 8 weeks. The parent or guardian will be instructed how to insert the ssNPA and will be encouraged to have the child wear it for increasing intervals while awake to allow the child to acclimate to wearing it. This will also prepare them for wearing the device during the night. If the child feels comfortable with the ssNPA, it will be kept in place during the day as well. Feedback from families regarding desensitization during the R61 phase will optimize the desensitization protocol for the R33 phase.

Demonstration and instruction will be provided on cleaning and suctioning (Appendix F); the latter is required for any build-up of nasal secretion, particularly during respiratory illness. Indeed, during periods of respiratory illness, the ssNPA may provide relief for breathing disturbances, as has been observed in our pilot patients. Adherence will be followed and fostered by a registered nurse with extensive experience in desensitization among children in the Pediatric Sleep Clinic who require PAP. Customized ssNPA desensitization will be modeled on our experience with PAP desensitization. These efforts to promote adherence will match or exceed what we routinely provide to achieve a PAP adherence rate of 60-70% in children.

Families will return to the clinic at weeks 2 and 4 to ensure optimal care and evaluate the device safety, tolerability, and acceptability. In between the clinic visits, regular contact will be made with families by the team, daily during the first week and weekly by the 2nd week (see Appendices H-K). During these calls, caregivers will report night to night witnessed apneas, improvement in daytime awareness, improvement in sleeping patterns of the patient, and any adverse events. Beside the two clinical visits at 2nd and 4th week, the number and frequency of extra visits will depend on: (1) the child's current threshold; and (2) how the child and family advance through each step of the desensitization protocol. The decision to hold on a particular step of the desensitization program will be based on whether the child's current level of anxiety or opposition is elevated. A recommendation to discontinue ssNPA treatment may be made if the child or family do not make progress with wearing the device in 2-4 weeks (depending on the number of visits during that time). Discontinuation of ssNPA therapy may occur after case consultation with other members of the study team to ensure that all strategies have been considered.

Evaluation of the device safety, tolerability, and acceptability will be assessed by a survey of patients and caregivers using a validated questionnaire with 10-point response scale (Appendix K). Mean and standard deviation scores as well as the percentage of those reporting satisfactory or better will be assessed. Device safety will be determined by adverse events

Table 3. Milestones for successful completion of the R61 phase

R61 Milestones	Goal (out of 5 subjects)
1. Device optimization and manufacturing in clean/sterile manner	100%
2. Parent report of ease of insertion; $\geq 5$ on Likert scale of 1-10	60% (3 of 5)
3. Child able to tolerate device in place	60% (3 of 5)
4. Child able to maintain device in place during sleep	60% (3 of 5)
5. Parent report of adherence based on diary	60% (3 of 5)
6. Comfort rating $\geq 6$ on Likert scale of 1-10	60% (3 of 5)

evaluation (Appendix L). Any possibly-related adverse events (e.g. nasal skin necrosis or device displacement) will be evaluated through clinical visits and caregiver's feedback using standardized case report forms. Milestones for the R61 phase are detailed in Table 3. Likert scale scoring will be used to assess ease of insertion, tolerability while in place, ability to maintain the device in place while sleeping, and comfort level. Information will be obtained from parents/caregivers. In addition to the listed milestones, open response feedback will be obtained from families to determine if design changes are required specific to this population that may improve usability.

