## **9.5 TREATMENT INTERRUPTIONS-DISCONTINUATION CRITERIA**

### ***9.5.1 Treatment Interruption Criteria***

In the event of patient illness, the patient will temporarily stop study treatment. Because nasal secretions and other upper respiratory symptoms can interfere with accurate data measurement and observation of treatment, the patient will have the option of pausing using the device until symptoms subside. Alternatively, if caregivers feel the device is providing symptomatic relief during the concurrent illness, they may continue use – however assessments, such as PSG will be postponed until resolution of acute illness to minimize artifact. Additionally, in the event of any temporary family emergency or necessary situation, the patient may also temporarily stop using the device. If for some reason there is a need for a different sized device, the treatment maybe paused while the new device is manufactured and delivered to the family. Observation will resume once the patient is treated with the new device.

The decision to hold on a particular step of the desensitization program will be based on whether the child's current level of anxiety or opposition is elevated. A recommendation to discontinue ssNPA treatment may be made if the child or family do not make progress with wearing the device in 2-4 weeks (depending on the number of visits during that time). Discontinuation of ssNPA therapy may occur after case consultation with other members of the study team to ensure that all strategies have been considered.

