### ssNPA User Feedback Questionnaire - DAILY

Thank you for participating in the ssNPA sleep study. Please let us know about you and your child's experience last night/yesterday using the ssNPA device by circling responses below:

1. Device insertion was....

- 1 - Extremely difficult
- 2 - Difficult
- 3 - Neutral
- 4 - Easy
- 5 - Extremely easy

2. Once placed, the device was...

- 1 – Not tolerated
- 2 – Poorly tolerated
- 3 - Neutral
- 4 – Tolerated
- 5 – Well-tolerated

3. During the night, the device came out completely and needed to be re-inserted...

- 1 – Very frequently
- 2 – Frequently
- 3 – Sometimes
- 4 – Rarely
- 5 – Not at all

4. During the night, the device came out partially and needed to be adjusted...

- 1 – Very frequently
- 2 – Frequently
- 3 – Sometimes
- 4 – Rarely
- 5 – Not at all

5. With the ssNPA, how many times did you have to get up during the night to optimize position of the device: \_\_\_\_\_

6. Please rate the level perceived comfort of your child wearing the device during the night...

- 1 – Very uncomfortable
- 2 – Uncomfortable
- 3 – Neutral
- 4 – Comfortable
- 5 – Very comfortable

7. If applicable, please rate the perceived comfort of the device during the day...

- 1 – Very uncomfortable
- 2 – Uncomfortable
- 3 – Neutral
- 4 – Comfortable
- 5 – Very comfortable

8. While using the device, my child's sleep was...

- 1 – Much less restful
- 2 – Less restful
- 3 - Stable
- 4 – More restful
- 5- Much more restful

9. While using the device, my child's snoring occurred...

- 1 – Much less often
- 2 – Less often
- 3 – Unchanged
- 4 – More often
- 5 – Much more

10. While using the device, my child's snores were...

- 1 – Much louder
- 2 – Louder
- 3 – Unchanged
- 4 – Quieter
- 5 – Much quieter

11. In the morning, my child appeared...

- 1 – Much more tired
- 2 – More tired
- 3 – Unchanged
- 4 – Less tired
- 5- Much less tired

Do you have any other comments or suggestions that you would like to share regarding your experience using the ssNPA?

---

\_\_\_\_\_

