### ssNPA User Feedback Questionnaire - WEEKLY

Thank you for participating in the ssNPA sleep study. Please let us know about you and your child's experience OVER THE PAST WEEK using the ssNPA device by circling responses below:

1. Device insertion was....

- 1 - Extremely difficult
- 2 - Difficult
- 3 - Neutral
- 4 - Easy
- 5 - Extremely easy

2. Once placed, the device was...

- 1 - Not tolerated
- 2 - Poorly tolerated
- 3 - Neutral
- 4 - Tolerated
- 5 - Well-tolerated

3. During the night, the device came out completely and needed to be re-inserted...

- 1 - Very frequently
- 2 - Frequently
- 3 - Sometimes
- 4 - Rarely
- 5 - Not at all

4. During the night, the device came out partially and needed to be adjusted...

- 1 - Very frequently
- 2 - Frequently
- 3 - Sometimes
- 4 - Rarely
- 5 - Not at all

5. With the ssNPA, how many times did you have to get up on average during the night to optimize position of the device: \_\_\_\_\_

6. Please rate the level perceived comfort of your child wearing the device during the night...

- 1 – Very uncomfortable
- 2 – Uncomfortable
- 3 – Neutral
- 4 – Comfortable
- 5 – Very comfortable

7. If applicable, please rate the perceived comfort of the device during the day...

- 1 – Very uncomfortable
- 2 – Uncomfortable
- 3 – Neutral
- 4 – Comfortable
- 5 – Very comfortable

8. While using the device, my child's sleep was

- 1 – Much less restful
- 2 – Less restful
- 3 – Stable
- 4 – More restful
- 5 – Much more restful

9. While using the device, my child's snoring occurred...

- 1 – Much less often
- 2 – Less often
- 3 – Unchanged
- 4 – More often
- 5 – Much more

10. While using the device, my child's snores were...

- 1 – Much louder
- 2 – Louder
- 3 – Unchanged
- 4 – Quieter
- 5 – Much quieter

11. In the morning, my child appeared...

- 1 – Much more tired
- 2 – More tired
- 3 – Unchanged
- 4 – Less tired
- 5 – Much less tired

Do you have any other comments or suggestions that you would like to share regarding your experience using the ssNPA?

4 of 4

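### The night-retention items in the day-one, daily and weekly surveys have no answer for a night without the device, so an unworn night can be scored as best retention

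*Combined protocol and SAP*

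**What the plan says.** Three parts of the plan make nights without the device foreseeable.

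- **Order of desensitization.** Section 9.2, Stage 2 has the child "get comfortable with placement of the device during daytime, after which, they will progress to use the ssNPA at night".
- **Holds.** The same section says "The decision to hold on a particular step of the desensitization program will be based on whether the child's current level of anxiety" (resistance by the child is the other ground) has risen. Stopping may be recommended only after 2 to 4 weeks without progress.
- **Pauses.** Section 9.5.1 states "In the event of patient illness, the patient will temporarily stop study treatment", although caregivers may continue if the device helps. It also allows a break for a family emergency and, when another size is needed, says "the treatment maybe paused while the new device is manufactured and delivered to the family".

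The forms are as follows.

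- Item 3 on Appendices I, J and K reads "During the night, the device came out completely and needed to be re-inserted". Item 4 reads "During the night, the device came out partially and needed to be adjusted". Both run from 1 (very frequent) to 5 (not at all).
- Item 5 on Appendix J asks for a count: "With the ssNPA, how many times did you have to get up during the night to optimize position of the device". Item 6 on Appendix I and item 5 on Appendix K are the equivalents.
- None of these items has a 'not used' answer, and no item on the three forms asks whether the device was worn at night. Only the daytime comfort item is marked as conditional.

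Both call scripts (Appendix H) ask how long the device was used, but a caregiver who has filled out the survey is taken past that question to the adverse-event part.

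Section 9.2 says Likert scoring will assess, among other things, whether the device stays in place during sleep. Milestone 4 in Table 3 concerns the same ability, with a goal of 3 of 5 children.

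**The concern.** On an unworn night the device did not come out, so 5 is a truthful answer to items 3 and 4, and zero is a truthful count of rises. Both are the best possible values. Once forms are pooled, a night when the device stayed in and a night when it was never inserted look the same. Children who are slow to reach night use, or who pause often, could then look like good retainers.

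At stake is the scaled evidence on retention during sleep. Items 3 and 4 are the only scaled retention items in the text supplied; the final questionnaire (Appendix M) has none. Section 4.2 makes optimizing the surveys for the larger study an R61 objective, so R61 is the time to correct them.

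**Working it through.** **No plan figure to reproduce.** The plan gives no number for this point. The check is a reading of the forms, followed by an illustration of size.

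**Step 1: what each form can record about an unworn night.**

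| Form | Items | Night items that accept a best value for an unworn night | Items recording night wear |
|---|---|---|---|
| Appendix I (day one) | 12 | 3 (items 3, 4, 6) | 0 |
| Appendix J (daily) | 11 | 3 (items 3, 4, 5) | 0 |
| Appendix K (weekly) | 11 | 3 (items 3, 4, 5) | 0 |

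**Step 2: does the phone call recover it?** Survey completed: the duration question is skipped in both scripts. Survey not completed: the question is asked, but the weekly version combines night and day use, so it does not isolate night wear.

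**Step 3: possible size on the nightly forms.** The documents give neither the number of unworn nights nor how caregivers would answer, so both are assumed. For one child:

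- N = nights with a form. I take 14, matching the two weeks of daily calls in Appendix H. Section 9.2 describes daily contact in week 1 only, so N = 7 is also shown.
- d = unworn nights; W = N − d; m = true mean score on worn nights.
- p = share of unworn nights answered 5; the rest are left blank.

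Recorded mean = (W·m + 5·p·d) / (W + p·d).
Shift = p·d·(5 − m) / (W + p·d).

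Example with N = 14, d = 3, m = 3:

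- p = 0.5: (33 + 7.5) / 12.5 = 3.24.
- p = 1: (33 + 15) / 14 = 3.43.

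| N | d | m | p = 0 | p = 0.5 | p = 1 |
|---|---|---|---|---|---|
| 14 | 3 | 2 | 2.00 | 2.36 | 2.64 |
| 14 | 3 | 3 | 3.00 | 3.24 | 3.43 |
| 14 | 3 | 4 | 4.00 | 4.12 | 4.21 |
| 14 | 7 | 2 | 2.00 | 3.00 | 3.50 |
| 14 | 7 | 3 | 3.00 | 3.67 | 4.00 |
| 14 | 7 | 4 | 4.00 | 4.33 | 4.50 |
| 7 | 3 | 2 | 2.00 | 2.82 | 3.29 |
| 7 | 3 | 3 | 3.00 | 3.55 | 3.86 |
| 7 | 3 | 4 | 4.00 | 4.27 | 4.43 |

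The shift is 0 when unworn nights are left blank. Its largest value here is 7 × (5 − 2) / 14 = 1.5 points. Excluding unworn nights returns the mean to m in every row.

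**Step 4: limits of the formula.** It describes one answer per night. Appendix K takes one answer per week, and in a partly worn week a caregiver would naturally answer about the nights of use. The formula does not apply to that form; the gap there is clearest for a week with no night use.

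**The case against.** **The planned summaries may not use these items.** For the Stage 2 questionnaire the plan says "Mean and standard deviation scores as well as the percentage of those reporting satisfactory or better will be assessed", and a reader might infer that these figures would be inflated. The documents do not establish that. The sentence belongs to a 10-point questionnaire cited as Appendix K, while Appendix K as supplied is a weekly 5-point form. The 10-point form is Appendix M, which has no retention item. The planned Likert assessment of retention remains, but without a formula or pooling rule. This objection stands.

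**Unworn nights may be known from elsewhere.** Section 9.2 gives adherence follow-up to a nurse and schedules clinic visits at weeks 2 and 4. Milestone 5 rests on a diary, section 10.2.2 expects daily adherence data from diaries, and section 11.6 requires device use records. The R33 active group sends bedtime and morning photos (section 9.4.1), and all caregivers can add comments. With 5 children in R61 the team may well know who has not reached night use. This stands in part: no text links these sources to the scoring of items 3 and 4, no listed appendix is a diary form, and the diary content stated in section 9.4.1 is sleep and wake times.

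**Nightly use is the stated aim.** Sections 2.2 and 11.3.1 favour it, and Stage 2 sends the child home with the device in place. This may reduce the number of unworn nights, but it does not remove the daytime-first order, the holds or the pauses.

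**The daily call script tells every caregiver to insert the device again that night.** A reader might infer a conflict with daytime-first desensitization. That depends on the desensitization protocol (Appendix G), which is not in the text supplied, and the line agrees with the nightly-use sections. I do not count it as a defect.

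**Conclusion.** The gap in the forms is established by their wording. The bias is possible but not demonstrated, and the point is minor. On the nightly forms, 3 to 7 unworn nights of 14 and worn-night means of 2 to 4 give an upward shift of 0 to 1.5 points on a 5-point scale. The result depends entirely on those assumptions and on how many caregivers enter 5 rather than leave the item blank.

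Three stronger readings are not supported:

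- **That milestone 4 would be falsely met.** No scoring rule ties items 3 and 4 to it, and its wording would not credit a child who never wore the device at night.
- **That every completed form is compromised.** Every form shares the gap, but only answers about unworn nights can be wrong, and their number is unknown.
- **That R33 efficacy is at risk.** The primary endpoint is the AHI response on the Week 8 PSG, which does not use these items.

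**What to change.** - Open Appendices I and J with: *Was the device used last night? (no / part of the night / all night)*. Add to Appendix K: *number of nights used in the past week*.
- Skip the night items when there was no night use.
- In both call scripts, ask about duration before the survey skip, with night and day asked separately.
- Report retention among nights used, together with the number of unworn nights and the reason: planned step or pause, or not tolerated.
- State that a child who never reaches night use does not meet milestone 4.

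**Cost.** Small edits to three short forms and two scripts, with no added visits or staff. Retention figures may look less favourable. Forms already collected can be reclassified only where a diary or call note shows whether the device was worn.

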## **10.2 Data Analysis**

### *10.2.1 R61 Phase:*

Analyses will be descriptive in the R61 phase of the study. The primary aim of the R61 phase is the 2nd generation ssNPA device confirmation and proof of concept that the ssNPA is tolerated and comfortable. For measures obtained using a 10-point scale including tolerability and comfort, we expect the margin of error for the mean estimate with 95% confidence to be 1.24 standard deviation. When tolerability and comfort measures are dichotomized (i.e., considering scores of 7 out of 10 as acceptable), the proposed sample size will give a margin of error of 0.19 for an estimate of proportion with positive responses.

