### **10.3 Outcome Criteria**

#### **10.3.1 R61 Phase:**

Criteria	Goal (out of 5 subjects)
Device optimization and manufacturing in a clean/sterile manner	100%
Parent/CG reported ease of insertion; $\geq 5$ on Likert scale of 1-10	60%
Child able to tolerate device in place	60%
Child able to maintain device in place during sleep	60%
Parent/CG report of adherence based on diary	60%
Comfort rating $\geq 7$ on Likert scale of 1-10	60%

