**ssNPA Sleep Study****Today's date:****ssNPA User Feedback Questionnaire**

Thank you for participating in the ssNPA sleep study. Based on your experiences over the last couple of months, please let us know about you and your child's experience using the ssNPA:

1. Overall, please rate the ease of insertion of the ssNPA:

Extremely easy 1 2 3 4 5 6 7 8 9 10 Extremely difficult

2. Overall, please rate your child's comfort with the device:

Extremely uncomfortable 1 2 3 4 5 6 7 8 9 10 Extremely comfortable

3. Please rate your child's overall sleep quality:

Worse sleep 1 2 3 4 5 6 7 8 9 10 Improved sleep

4. Overall, please rate your child's behavior during the day after using the ssNPA:

Worse than normal 1 2 3 4 5 6 7 8 9 10 Better

5. Please rate how you think the ssNPA works for your child's sleep:

Not effective 1 2 3 4 5 6 7 8 9 10 Effective

6. How likely are you to use this device for your child?

Highly unlikely 1 2 3 4 5 6 7 8 9 10 Definitely

Please provide any comments or suggestions you have regarding the device:

---

---

---

---

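### Two R61 milestones cannot be scored as written: comfort is cut at 6 in Table 3 but at 7 in section 10.3.1, and the ease-of-insertion rule runs against the only 1–10 insertion item supplied

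*Combined protocol and SAP*

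**What the plan says.** The R61 milestones appear twice, in Table 3 of section 9.2 (Stage 2) and in the criteria table of section 10.3.1. Both set a 60% goal among five subjects for the rating milestones.

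- **Comfort.** Table 3 has "Comfort rating $\geq 6$ on Likert scale of 1-10". Section 10.3.1 has "Comfort rating $\geq 7$ on Likert scale of 1-10". Section 10.2.1, where it dichotomizes tolerability and comfort, speaks of "considering scores of 7 out of 10 as acceptable".
- **Ease of insertion.** Table 3 has "Parent report of ease of insertion; $\geq 5$ on Likert scale of 1-10", and section 10.3.1 uses the same cut-off of 5.
- **The instruments.** The text above Table 3 says evaluation is by a survey "using a validated questionnaire with 10-point response scale (Appendix K". The weekly survey printed as Appendix K has five response options per rating item; for insertion the top one is "5 - Extremely easy". The final User Feedback Questionnaire (Appendix M according to the contents list and Stage 3) is on 1–10. Its item 1, insertion, reads "Extremely easy 1 2 3 4 5 6 7 8 9 10 Extremely difficult". Its item 2, comfort, reads "Extremely uncomfortable 1 2 3 4 5 6 7 8 9 10 Extremely comfortable".
- **Timing.** Section 9.3 schedules tolerability surveys in several periods. Under Stage 3, the parent completes the final questionnaire after a call reporting the PSG result.
- **Use.** Section 9.4 begins R33 recruitment after R61 has been completed successfully.

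**The concern.** A milestone that controls progress to the next phase should give one answer for one set of forms. Here a comfort rating of 6 passes in one section and fails in the other. The insertion milestone, applied to the item as printed, credits difficulty and penalizes ease. Comfort runs in the favourable direction on the same form, so a single scoring convention cannot serve both items.

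The milestone rows also do not say which form, or which of several time points, supplies the rating. With five children each rating is worth 20 percentage points, so an open choice of cut-off, direction or form, made after the ratings are seen, can decide whether the milestone is met. Tolerability and comfort are part of the R61 primary aim in section 10.2.1, so these are not side measures. If the final questionnaire is the source, its ratings are given with the PSG result known and may be coloured by whether the device worked.

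**Working it through.** **Plan's own figure.** 3/5 = 0.60, which reproduces the 60% goal.

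**General rule.** At least 3 of 5 ratings are at or above c exactly when the third-highest rating, the median of five, is at or above c.

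**Comfort.** Inputs: cut-off 6 (Table 3) and 7 (10.3.1).
- Table 3 is met when the median is ≥ 6; 10.3.1 is met when the median is ≥ 7.
- They disagree exactly when the median is 6.

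| Ratings (illustrative) | Count ≥ 6 | Table 3 | Count ≥ 7 | 10.3.1 |
|---|---|---|---|---|
| 6, 6, 6, 4, 3 | 3/5 | met | 0/5 | missed |
| 8, 7, 6, 5, 4 | 3/5 | met | 2/5 | missed |

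For a sense of scale, suppose a child's chance of passing is 0.60 at cut-off 6 and 0.40 at cut-off 7. These are assumed values. The chance of at least 3 of 5 is 10p³(1−p)² + 5p⁴(1−p) + p⁵:
- p = 0.60: 0.3456 + 0.2592 + 0.0778 = 0.683.
- p = 0.40: 0.2304 + 0.0768 + 0.0102 = 0.317.
- With 0.80 and 0.60 instead, the two chances are 0.942 and 0.683.

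**Insertion.** Inputs: cut-off 5 (both tables); item 1 with 1 = easiest and 10 = most difficult.
- Literal rule, x ≥ 5: responses 5 to 10 pass. The milestone is met when the median is ≥ 5.
- Reversed rule, 11 − x ≥ 5, that is x ≤ 6: responses 1 to 6 pass. The milestone is met when the median is ≤ 6.
- Responses 1–4 and 7–10, eight of the ten options, change status. Only 5 and 6 pass both ways.
- The two scorings disagree unless the median is 5 or 6.

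| Responses (illustrative) | Literal | Reversed |
|---|---|---|
| 2, 2, 3, 4, 8 (mostly easy) | 1/5, missed | 4/5, met |
| 8, 8, 9, 2, 3 (mostly difficult) | 3/5, met | 2/5, missed |
| 10, 10, 10, 10, 10 | 5/5, met | 0/5, missed |

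Listing all 2,002 unordered sets of five ratings from 1 to 10 confirmed both median statements without exception.

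**Which form can supply the ratings.** The day-one, daily and weekly surveys rate insertion and comfort on 1–5. On those, a comfort rating of 6 or 7 is impossible and an insertion rating of 5 is the top category alone. Only the final questionnaire has 1–10 items for both, and section 5.1 ties these scales to the study debriefing.

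**Number of ratings.** Section 10.4 plans to enrol 7 to obtain 5 completers (5/0.8 = 6.25, so at least 7), while section 11.8.1 recruits up to 5. If six or seven children supplied ratings, 60% would be 3.6 or 4.2, so 4 of 6 or 5 of 7 would be needed, and one rating would be worth 16.7 or 14.3 points. The median rule above is for exactly five.

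**The case against.** The strongest objection concerns the insertion item. Neither milestone table cites the final questionnaire. The rows name the construct as ease, which on its face means higher is easier, and they follow a reference to Appendix K, whose insertion item does run in that direction. The inversion is therefore an inference about the source item, and an analyst who looked at the printed anchors would probably notice it. It is true that the source is inferred. But Appendix K cannot yield a 1–10 rating, the final questionnaire is the only form supplied that can, and no scoring rule guards against the literal reading.

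On comfort, the conflict affects the outcome only when the median is exactly 6, and the 7 in section 10.2.1 is an aside to a margin-of-error statement rather than a milestone definition. Both points are fair. The conflict between Table 3 and section 10.3.1 does not depend on section 10.2.1.

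On timing, caregivers already see snoring and apneas every night, so they have a view of benefit before the results call. How much the result would shift insertion and comfort ratings is not known. That point is conditional and secondary, and the enrolment mismatch is minor.

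**Conclusion.** The concern holds. The two comfort cut-offs are a direct contradiction: same milestone, same scale, same goal, and nothing says which governs. It decides the outcome when the median of five ratings is 6. The insertion milestone is inverted if item 1 of the final questionnaire is its source, which is the only reading the supplied forms allow; literal scoring then gives the wrong answer for any median other than 5 or 6. The rating sets shown are illustrative, since the documents contain no R61 ratings, and they assume five ratings.

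The reach is limited. R61 analyses are descriptive, no text says that one missed milestone stops R33, and the R33 primary outcome is untouched. It should be fixed because these milestones define R61 success and the correction is nearly free.

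**What to change.** 1. Put one comfort cut-off in Table 3, section 10.2.1 and section 10.3.1, fixed before R61 ratings are reviewed. If R61 is already complete, report the result at both 6 and 7. Settling on 7 makes the milestone harder than Table 3 now states.
2. State that item 1 of the final questionnaire is scored as 11 minus the response before the cut-off of 5 is applied. Re-anchor the printed item instead only if no forms have been completed.
3. Correct the description of Appendix K in Stage 2, and name the form and time point that supply the insertion and comfort milestones.
4. If the final questionnaire is the source, have parents complete it before the PSG results call, for example at the 8-week visit in section 9.3.
5. As a minor item, reconcile the R61 enrolment in section 11.8.1 with section 10.4, and state the required count if more than five children supply ratings.

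The cost is wording edits, a one-line recode and a change in the order of two existing steps, with no extra visit. One trade-off remains: a child with no 8-week PSG may have no final form. The weekly survey is completed during use and would avoid that, but it would need 1–10 items added.
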